Investigating the effects of cuing medication availability on patient-controlled analgesia pump usage in pediatric patients: Results of a randomized controlled trial

NCT02456909

Date of Document: March 30, 2015

Study Protocol and Statistical Analysis Plan

Materials and Methods

This single-center, prospective, RCT was conducted at a large children's hospital in the Midwest. The study was approved by the hospital Institutional Review Board, and was registered at www.clinicaltrials.gov (ID: NCT02456909) by the principal investigators prior to study enrollment. Enrollment was April 2015 – August 2017.

Participants

Potential participants between the ages of 7 – 17 years, undergoing an orthopedic, abdominal or thoracic surgery for which PCA is routinely prescribed for post-operative pain management, were identified from the hospital surgery schedule. Eligible patients were opioid naïve, and patients and at least one parent were able to read and speak English. Exclusion criteria included 1) prior experience with PCA, 2) cognitive delay precluding independent use of the PCA button, or 3) pre-operative use of a daily anxiolytic or antidepressant medication.

Procedures

Recruitment and Randomization

Patients were approached immediately prior to surgery. After informed consent and assent were obtained, participants were randomized into either the control group or the experimental “light” group and were stratified by gender and surgical procedure (orthopedic, abdominal, or thoracic) in blocks of 4. The randomization scheme was created by a statistician on the research team using Windows version 6.0 of “rand.exe” (<http://block-stratified-randomization.software.informer.com>). Participants were enrolled by the clinical research coordinator, who used the scheme to assign participants to groups after consent. Recruitment continued until each group included 60 completed participants (defined as having completed at least 24 hours of PCA use and completed assessment of the primary outcome). Carefusion

Alaris™ PCA pumps were used for all patients. The PCA profile (i.e. configuration of the light cue operation) for both groups was set up by a nurse in the post-anesthesia care unit (PACU). The starting opioid dose is standardized, and was set up by the PACU nurse. For the control group, the PCA pump was used according to the hospital's standard operating procedures: The PCA emitted a "beep" with every button press, and the status of the green light on the button never changed (i.e., it remained continually lit). For the light group, the PCA pump was configured so that the PCA button only emitted a "beep" when a button press resulted in successful opioid delivery. The green light on the button flashed during opioid delivery, was darkened immediately after delivery and was illuminated at the end of the lockout period, indicating a dose was ready to be delivered. Treatment of side effects was determined by the floor nurse who was not a member of the study team. To ensure consistent messaging, patients and parents in both groups were given scripted instructions regarding PCA use. The patient and guardian were also given a printed copy of the instructions prior to surgery.

PCA monitoring and Pain assessments

Either morphine or hydromorphone (converted to morphine equivalents) was administered using PCA for both groups as prescribed by the anesthesia service. Using morphine equivalents, our standardized PCA orders are as follows: 20 mcg/kg for the PCA dose and basal (if used), 8 minute lockout, and a 120 mcg/kg hourly maximum.

Patients had continuous pulse oximetry. Pain and sedation scores were recorded every 2 hours for the first 24 hours, with a minimum of every 4 hours thereafter. PCA use, including injections (i.e. button presses resulting in delivered doses) and attempts (i.e. button presses during the lockout period), were documented hourly by a nurse who was not a member of the study team. If for some reason the nurse was unable to document the hourly number of

injections and attempts (e.g. busy with another patient), the following hour's data would reflect the previous 2 hours' worth of attempts and injections.

Data collection terminated when the PCA was discontinued, or up to 60 hours post-surgery, whichever came first. The study period was defined as beginning when the patient arrived in the Post-Anesthesia Care Unit (PACU) through Post-Operative Day (POD) 2.

Measures

All outcomes were collected on post-operative days (PODs) 0-2, with the exception of state anxiety on POD 0, which was collected prior to surgery in the pre-op holding area. The research coordinator administered the STAI once on each POD, and also extracted all other data from the participant's electronic health record (EHR).

Demographics, anthropometrics, and treatment

Demographics (age, sex, race and ethnicity) and anthropometrics (height, weight, and BMI percentile) were extracted from the EHR. Benzodiazepine (lorazepam, diazepam), acetaminophen, ibuprofen, and ketorolac use and intraoperative methadone administration were also extracted from the EHR. These data were collapsed across PODs, and reported as presence/absence. Pre-existing chronic pain was also extracted from the EHR and reported as presence/absence.

Primary Outcome: Patient satisfaction with pain management

The primary outcome was the patient's response to a single question, focused specifically on satisfaction with pain management: "*How satisfied were you with your pain management (was your pain well controlled)?*," with 0 = "very dissatisfied" and 10 = "very satisfied". Participants answered additional questions to rule out factors that could potentially explain between-group similarities or differences in opioid consumption (e.g. Did you

understand how to use the pain pump?). These questions were completed independently by the patient within 24 hours of the end of the study period. Questions were developed by experts in pediatric pain management and were based on the study by Patak et al.¹

Secondary Outcomes

Opioid consumption and opioid-related side-effects

Data on opioid consumption and treatment of related side effects were extracted from the EHR. Total opioid consumed via PCA was calculated from all opioid delivered via the basal rate and via injections, and is reported in mg/kg/hr. Hydromorphone was converted to morphine equivalents by multiplying the total amount of hydromorphone consumed (mg) by 5.²

Data on side effects requiring treatment included nausea/vomiting, pruritus, over sedation (using the Children's Hospital of Wisconsin Sedation Scale,³ and respiratory depression. Treatment was coded as yes/no for each POD.

Pain intensity

Pain scores: Pain scores were recorded from the time patients left the PACU until discontinuation of the PCA or through POD 2 (whichever came first) and were extracted from the EHR. Pain was assessed using the age appropriate, hospital approved pain scale. Children either used a 0-10 (0 = no pain, 10 = worst pain possible) numeric rating scale, or the 0-10 Faces Pain Scale-Revised [10].

PCA usage

The total number of hourly injections and attempts were extracted from the EHR.

State Anxiety

The Spielberger State-Trait Anxiety Inventory for Children (STAIC), state version, is a well-validated 20 item questionnaire used to assess anxiety about a current situation or impending event⁴. Each question begins with the stem “I feel...” and ends with 3 choices (e.g., “very calm,” “calm,” “not calm”). Respondents are instructed to consider “*how you feel right now.*” A total score is computed from a sum of the items, with scores ranging from 0 – 60. The STAIC was administered by the research coordinator once before surgery (POD 0) and once per day on POD 1 and POD 2. Elevated state anxiety was based on T-scores and was defined as ≥ 1 standard deviation above the mean.⁵

Power Analysis:

An *a priori* sample size calculation was based on the primary outcome. Rahman et al. examined patient satisfaction with pain relief for those randomized to pain management with PCA vs. intravenous boluses of analgesia titrated to patient comfort levels.⁶ Based on a 1-5 scale (1 = excellent, 5 = disappointing), the average pain relief rating for patients in the PCA group was significantly better at 2.0 (± 0.37) than the rating for patients in the control group at 3.0 (± 0.24). With a power of 80%, a type I error rate (alpha) of 0.05, and a two-tailed t test, 60 patients would have been needed in each group to detect a difference of at least 0.16 SD between the light and control groups.

Statistical Analysis

Modified intent-to-treat analyses included all randomized participants, with the exception of those who did not receive the allocated intervention, as shown in Figure 1. Means and standard deviations or median and interquartile range (IQR) when data were skewed, were used for continuous data, and categorical items were described using frequency statistics. A Chi-square test or a Fisher’s exact test was used to explore the relations between categorical variables, and bivariate correlations (Pearson correlation test) were used to explore correlations

between continuous variables. Comparisons between intervention and control groups and between age groups [children (≤ 12 years) and adolescents (13-17 years)] were conducted using a Mann-Whitney test. Missing data were treated using listwise deletion, and assumed to be missing completely at random. A two-sided p-value <0.05 was used to define what was considered significant.

Multivariable analyses using a mixed model with random time were used to examine the effect of the intervention group and age group on two dependent variables (DV): 1) opioid consumption over time and, 2) injections:attempts ratio over time. The independent covariates (IV) considered were pain scores, methadone use and the interaction between methadone use and intervention group, age group, intervention group, and the interaction between age group and intervention group. A backward model selection procedure was used, with a p-value <0.05 as a criterion to keep the variable in the multivariable model. Based on this criterion, the interaction between intraoperative methadone and intervention group was dropped from the model. The DV opioid consumption was transformed using square root to satisfy model assumptions. The parameters were estimated using Maximum likelihood, and unstructured covariance structure was used for repeated measurements. The mixed model with random effects allows for missing data, under the assumption that data were missing at random. Statistical analyses were calculated using SPSS 24 (IBM SPSS Inc., Chicago, IL) and SAS 9.4 software (SAS Institute Inc., Cary, NC).

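### The factors used to stratify randomization, gender and surgical procedure, appear in neither the between-arm test nor the mixed models (a minor loss of efficiency)

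*Combined protocol and SAP*

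**What the plan says.** Under Recruitment and Randomization, participants are "stratified by gender and surgical procedure (orthopedic, abdominal, or thoracic) in blocks of 4". Two genders by three procedures gives 6 strata. The same section sets the stopping point: "Recruitment continued until each group included 60 completed participants".

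Under Statistical Analysis:

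- Between-arm test: "Comparisons between intervention and control groups and between age groups" use a Mann-Whitney test, with no stratification or adjustment stated. It is the only between-arm test named that fits the 0-10 satisfaction item, the primary outcome.
- Mixed models (opioid consumption; injections:attempts ratio): "The independent covariates (IV) considered were pain scores, methadone use and the interaction between methadone use and intervention group". The list goes on to age group, arm and their interaction, and ends there. Gender and surgical procedure are not on it, and no other section brings them into an analysis.
- Selection: "A backward model selection procedure was used, with a p-value <0.05 as a criterion to keep the variable in the multivariable model". It is then reported that "the interaction between intraoperative methadone and intervention group was dropped from the model".
- Analysed patients: "Modified intent-to-treat analyses included all randomized participants, with the exception of those who did not receive the allocated intervention", and "Missing data were treated using listwise deletion".

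**The concern.** Blocking within strata removes most chance imbalance between arms on the stratification factors. If those factors predict the outcome, the arm difference varies less from trial to trial than an analysis ignoring them assumes. The standard error is then too large, the true type I error falls below 5%, and power is lost. Here both factors the trial chose to balance are absent from the analysis, while age group, which was not a stratification factor, is a candidate. Backward selection cannot rescue a factor that was never a candidate.

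What is at stake is efficiency. If the strata are not prognostic, a stratified analysis gains nothing and costs a little. A further question is whether blocks stay intact among analysed patients, given the completer-based stopping rule, the modified intent-to-treat exclusions and the listwise deletion.

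**Working it through.** **Inputs from the documents.** 6 strata, blocks of 4, two arms, 60 completers per arm, two-sided alpha 0.05, 80% power.

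**Inputs assumed.** R2 from 0 to 0.30; gender 50/50; surgery mix equal thirds, 60/25/15 or 80/12/8; random exclusions of 0 to 30%. The documents give none of these.

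**The plan's own figure, and the effect size used.** With n = 2(1.96 + 0.842)²/d², the stated 0.16 SD gives n = 614 per group, not 60. Read instead as 0.16 points with pooled SD √((0.37² + 0.24²)/2) = 0.312, d = 0.16/0.312 = 0.513 and n = 60. That mismatch in the Power Analysis is a separate issue and nothing here rests on it. It does mean the effect size must be a reference value: 0.513 SD in the formula check and 0.515 SD in the simulation. The latter is the effect a t test with 60 per arm detects with 80% power.

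**Formula check (balanced strata, normal outcome).** With s = √(1 − R2) and SE = √(2/60) = 0.1826:

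- Type I error, unadjusted = 2[1 − Φ(1.96/s)]
- Power, unadjusted = Φ[(d/SE − 1.96)/s]
- Power, adjusted = Φ[d/(SE·s) − 1.96]

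At R2 = 0.10, s = 0.949 and d/SE = 0.513/0.1826 = 2.81. Type I error is 2[1 − Φ(2.066)] = 3.9%, unadjusted power Φ(0.896) = 81.5%, and adjusted power Φ(1.002) = 84.2%.

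| R2 | Type I error, unadjusted | Power, unadjusted | Power, adjusted |
|---|---|---|---|
| 0 | 5.0% | 80.2% | 80.2% |
| 0.05 | 4.4% | 80.8% | 82.2% |
| 0.10 | 3.9% | 81.5% | 84.2% |
| 0.20 | 2.8% | 82.9% | 88.1% |
| 0.30 | 1.9% | 84.5% | 91.9% |

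**Simulation of the actual design.** There were 20,000 trials per setting, with permuted blocks of 4 in 6 strata and recruitment until each arm had at least 60 completers. Strata effects were additive and satisfaction was rounded and clipped to 0-10. The rank model regresses midranks on arm, gender and procedure. Ranges run over the surgery mixes and exclusion rates.

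| R2 | Mann-Whitney type I error | Power change, van Elteren (points) | Power change, rank model (points) | Power change, mixed-model approximation (points) |
|---|---|---|---|---|
| 0 | 4.9-5.5% | −1.5 to −1.1 | −0.3 to 0.0 | −0.4 to −0.1 |
| 0.05 | 4.3-4.8% | 0.0 to +0.8 | +1.2 to +1.5 | +1.1 to +1.4 |
| 0.10 | 3.9-4.4% | +1.6 to +2.1 | +2.6 to +2.9 | +2.6 to +2.9 |
| 0.20 | 3.0-3.7% | +4.8 to +5.5 | +5.6 to +6.3 | +5.3 to +6.2 |
| 0.30 | 2.1-3.0% | +7.8 to +8.9 | +7.8 to +9.4 | +7.5 to +8.8 |

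The stratified alternatives hold type I error at 4.7-5.5%. The last column compares a linear model on one mean per patient with and without the two factors. There R2 is the share of between-patient variance that the strata explain beyond the retained terms. Repeated measures, pain scores, methadone and age group are not simulated. Monte Carlo SE is about 0.15 points for null rates, 0.3 for power, and 0.06-0.23 for the paired van Elteren and rank-model differences.

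**Broken blocks.** At R2 0.30 and a 60/25/15 mix, with 0, 10, 20 and 30% excluded at random, Mann-Whitney type I error is 2.2, 2.4, 2.5 and 3.0%, and the van Elteren gain is 8.2, 8.2, 8.7 and 8.8 points. Exclusions reduce the conservatism only partly and do not shrink the gain.

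**The case against.** No rule is broken. The plan never promises a stratified analysis, and an unstratified rank test after stratified randomization is valid. That stands, and it is why the point is graded as optional.

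The benefit depends on an R2 that nothing in the documents supports, least of all 0.20-0.30 for a single satisfaction item. This also stands. At R2 0.05 or less the gain is 1.5 points or under, and the van Elteren test loses slightly at R2 0. The covariate-adjusted models nevertheless risk at most 0.4 points.

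The simulation uses one effect size. The same formulas, with both rejection tails counted, give gains from adjustment at R2 0.10 of 2.4 points at 0.16 SD, 4.1 at 0.30 SD and 2.7 at 0.515 SD. At R2 0.30 the gains are 8.4, 14.9 and 7.3. The quoted ranges therefore do not bound the gain, which can be larger at other effects; the decimals should not be over-read.

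The mixed-model figures are patient-level approximations. If pain scores or methadone use already differ by procedure, the strata may explain less of what remains. That limitation stands.

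Finally, the text reads as retrospective: enrollment is reported as complete and a model term as already removed. An addition made now cannot recover power for the primary comparison. That limits the remedy to supportive results but does not remove the point.

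**Conclusion.** The concern holds as a minor efficiency point. The plan stratifies on two factors and then uses neither. Omitting them does not inflate type I error or bias the arm comparison; that statement concerns the omission only, since exclusions were assumed non-differential between arms.

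For the covariate-adjusted analyses at the reference effect, the loss from omission is about 1 to 3 points of power for R2 between 0.05 and 0.10, 5 to 6 at 0.20, and 7.5 to 9.4 at 0.30. It is nil if the strata are not prognostic. Additive strata effects in the simulation favour the additive rank model. Confidence is medium because R2 and the stratum sizes are unknown.

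**What to change.** 1. Mixed models: keep gender (1 df) and surgical procedure (2 df) as fixed terms in both models, exempt from the p<0.05 backward selection. That is 3 df per model. The power cost if neither is prognostic is about 0.1-0.4 points in the patient-level approximation.
2. Satisfaction: beside the Mann-Whitney result, report a rank or ordinal model with arm, gender and procedure, or a van Elteren test over the 6 strata. If the strata are not prognostic, the rank model costs 0-0.3 points in these simulations and the van Elteren test 1.1-1.5. Treat the added result as supportive; it should not displace the Mann-Whitney for the primary outcome.
3. Label as post hoc any of these analyses chosen after the data were seen.

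No new data are needed, because both factors had to be known to randomize, and the programming change is small.

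### The coordinator who enrols patients also applies a fixed block-of-4 scheme with no concealed release described, so upcoming assignments could be known or partly predicted before approach

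*Combined protocol and SAP*

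**What the plan says.** All of this is in the combined protocol and SAP.

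- **Generation** (Recruitment and Randomization): "The randomization scheme was created by a statistician on the research team". Participants are "stratified by gender and surgical procedure (orthopedic, abdominal, or thoracic"), which makes 2 × 3 = 6 strata, with one block size, 4.
- **Enrolment and assignment** (same section): "Participants were enrolled by the clinical research coordinator", "who used the scheme to assign participants to groups after consent". No sealed envelopes, web or phone release, or independent holder of the list is mentioned.
- **Timing** (Participants; Recruitment and Randomization): candidates "were identified from the hospital surgery schedule". "Patients were approached immediately prior to surgery".
- **Visibility of the arm** (Recruitment and Randomization): for controls, "the status of the green light on the button never changed (i.e., it remained continually lit"), and every press beeps. In the light group the light flashes, goes dark and comes back on, and the pump beeps only when a dose is delivered. No blinding is described.
- **Analysis** (Statistical Analysis): arms are compared with a Mann-Whitney test, which makes no adjustment for baseline variables.

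**The concern.** Allocation concealment protects the decisions taken before consent: whom to approach from the surgery list, and how hard to recruit. Assigning after consent does not protect those decisions if the person making them can already see or work out the next assignment.

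The written procedure gives enrolment and assignment to one role. Even with the list hidden, that role learns every assignment as it is made. The surgical procedure, and in practice the sex, of the next candidate would be known beforehand, so the stratum is known too. With one fixed block size, the end of each block can then be worked out.

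What is at stake is selection at entry. If patients expected to do well are recruited more readily when one arm is due, the groups differ at baseline, and an unadjusted comparison of satisfaction carries that difference into the result.

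**Working it through.** The plan gives no figure for predictability, so there is none to reproduce. The sample-size statement enters only through its 60 per group.

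**Inputs.** From the document: block size 4, six strata, 60 completed participants per group (120 in total), two-sided alpha 0.05. Assumed: 1:1 allocation (inferred from the equal targets), and the size of any steering, on which the document is silent.

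**1. Predictability in blocks of 4.** There are 6 equally likely orders of AABB, hence 6 × 4 = 24 positions. A position is certain when one arm is already used up.

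| Position in block | Certain (of 6 orders) | Best guess correct |
|---|---|---|
| 1 | 0 | 1/2 |
| 2 | 0 | 2/3 |
| 3 | 2 | 2/3 |
| 4 | 6 | 1 |

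Certain: (0 + 0 + 2 + 6)/24 = 8/24 = 33.3%. Best guess: (1/2 + 2/3 + 2/3 + 1)/4 = 70.8%, against 50% by chance. Simulating 120 patients over six strata, with incomplete last blocks allowed, gives about 38 certain assignments (95% range 32 to 43). With the list visible, the figure is 100%.

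**2. Consequence under assumed steering.** Let patients entering the predictable third differ by s SD in favour of the expected arm, in opposite directions for the two arms.

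- Bias = (1/3) × 2s.
- Shift of the test statistic: δ = bias / √(2/60), where √(2/60) = 0.183.
- Type I error = P(Z > 1.96 − δ) + P(Z < −1.96 − δ).

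| s (SD) | Bias (SD) | δ | Type I error |
|---|---|---|---|
| 0.10 | 0.067 | 0.365 | 6.5% |
| 0.25 | 0.167 | 0.913 | 15.0% |

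The t distribution with 118 degrees of freedom gives 6.5% and 14.8%. These are normal-theory figures, used as an approximation to the planned Mann-Whitney test.

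**3. What varied blocks achieve.** With block sizes drawn at random from 4, 6 and 8, the individual sizes undisclosed, and 20 patients per stratum, an observer who updates optimally on the stratum history is certain of about 2% of assignments and guesses about 67% correctly.

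**4. Power of a retrospective check.** Take 38/2 = 19 predictable and 60 − 19 = 41 other patients per arm. Compare the arm difference in satisfaction between the two sets. The contrast is 2s, with standard error √(2/19 + 2/41) = 0.392.

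- s = 0.25: 0.50/0.392 = 1.27, power about 25%.
- s = 0.10: 0.20/0.392 = 0.51, power about 8%.

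**The case against.** A reader might infer that the coordinator held an open list, so that the sequence was unconcealed by design. The text does not say so. It separates generation by the statistician from use by the coordinator, and it places assignment after consent. A coordinator opening sealed envelopes prepared by the statistician would fit the same sentence. The 100% case is therefore conditional. So is the 33% and 71% case: nothing says that the coordinator knew the block size or tracked six strata, although both are feasible for the person making every assignment.

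A reader might also take 15% as the expected type I error. It rests on 0.25 SD of steering, for which the document gives no basis. A patient's stratum is fixed, so steering can work only through who is recruited. Suppose the recruiter selects by a cut-off on a normally distributed trait, visible before surgery, that correlates r with later satisfaction. A shift of 0.25 SD then requires losing about 74%, 52% or 30% of eligible patients in each predictable slot at r = 0.2, 0.3 or 0.5. A shift of 0.10 SD requires about 30%, 19% or 10%. The lower end of the range is easier to believe.

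Finally, the subjective rating tempts one to argue that unblinding makes the problem worse. That is a separate response bias, which concealed allocation would not remove. The satisfaction questions are completed by patients on their own, and instructions are scripted in both arms, which limits the coordinator's later influence on the primary outcome.

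These limits stand. They do not remove the weakness in the stated procedure: one role enrols and assigns, the block size is fixed, and no safeguard is described.

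**Conclusion.** The point holds as a weakness of the written procedure, not as evidence of bias. Upcoming assignments could be known if the list was visible. If it was hidden but the block size and stratum history were known, they could be partly predicted: 33% certain, 71% best guess. Under assumed steering of 0.10 to 0.25 SD each way in the predictable third, the bias would be 0.07 to 0.17 SD and the type I error 6.5% to 15%. The document does not show that the list was open, that blocks were tracked or that any steering took place. That the trial was open-label is itself an inference, from the perceptible cues and the absence of described blinding. The change is worth making because it is cheap and standard, and because selection at entry cannot be reliably undone in the analysis.

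**What to change.** **Main change, for any further or repeat use of the design.** The statistician, or another existing team member who does not enrol, keeps the list. That person releases one assignment at a time after consent is logged, by sequentially numbered opaque sealed envelopes or by web or phone. This needs some preparation but no extra staff or patients.

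**Secondary change.** Generate the list with randomly varied block sizes (for example 4, 6, 8) within the same six strata, and do not disclose them. This cuts certain assignments from 33% to about 2%, but best-guess accuracy only from 71% to 67%, so it does not replace separating the list-holder from the enroller. The cost is a slightly larger possible imbalance at the end of a stratum.

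**For data already collected.** Enrolment is reported as complete (April 2015 to August 2017), so a new list cannot help this trial. State who held the list, what the coordinator could see and how each assignment was released. If release was not concealed, report that as a limitation. Baseline variables and satisfaction can be tested against the assignment probability implied by block history, using existing data. On satisfaction the power is only about 8% to 25% over the range above, and the check is poorly matched to an open list, where every assignment is knowable. A null result should not be presented as reassurance.

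### Over-sedation and respiratory depression are counted through treatment given, so over-sedation that was charted but not treated is likely to be missed

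*Combined protocol and SAP*

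**What the plan says.** Under Secondary Outcomes (Opioid consumption and opioid-related side-effects), the source is described thus: "Data on opioid consumption and treatment of related side effects were extracted from the EHR". The events are listed as "Data on side effects requiring treatment included nausea/vomiting, pruritus, over sedation", followed by a parenthesis naming the hospital's own sedation scale, and then respiratory depression. The coding rule is "Treatment was coded as yes/no for each POD". No scale cut-off is given, nothing says how a score and a treatment combine to make an event, and respiratory depression is not defined.

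Under Recruitment and Randomization, in the paragraph on pump set-up, the decision to treat is assigned: "Treatment of side effects was determined by the floor nurse who was not a member of the study team". The same paragraph describes how the arms differ at the bedside. In the control arm the button sounds at every press and stays lit. In the light arm it sounds only when a dose is delivered, and "The green light on the button flashed during opioid delivery, was darkened immediately after delivery and was illuminated at the end of the lockout period".

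Under PCA monitoring and Pain assessments, the plan states "Pain and sedation scores were recorded every 2 hours for the first 24 hours, with a minimum of every 4 hours thereafter". It also says that pulse oximetry was continuous, and that injections and attempts "were documented hourly by a nurse who was not a member of the study team".

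**The concern.** The recorded variable is a care decision, not the event. For nausea/vomiting and pruritus the documents mention no other regular measurement, so treatment may be the best record available. Over-sedation is different, because a scheduled score exists. A child whose score showed over-sedation, but who had no treatment coded, counts as free of the event.

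This matters because the intervention tells opioid-naive children when the next dose can be had. Opioid consumption is itself a secondary outcome, and opioid-related harm is its natural counterpart. A finding of no difference on this outcome would be read as no difference in over-sedation, when the data can show only no difference in treatment. If the readiness to treat differed between arms, that difference would also pass into the comparison.

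**Working it through.** The plan states no side-effect rate, and no power statement concerns this outcome, so there is no figure to reproduce. The check is mainly a comparison of sections.

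**What is measured and what is counted**

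| Component | Regular measurement described | What the outcome counts |
|---|---|---|
| Over-sedation | Sedation scores every 2 h for 24 h, then at least every 4 h | Treatment yes/no per POD |
| Respiratory depression | Continuous oximetry; charting of values not stated | Treatment yes/no per POD |
| Nausea/vomiting, pruritus | None described | Treatment yes/no per POD |

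Completed participants had at least 24 hours of PCA (Recruitment and Randomization). The schedule therefore implies 24 / 2 = 12 sedation scores per child in that period, or 12 × 120 = 1,440 for 60 per group. This shows what material exists. It is not evidence that events were missed.

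**Illustration of missed events.** The rates are assumptions. Take one potential event per child, a true rate p in both arms, and a probability s that an event is treated.

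- Recorded rate = p × s
- Expected cases missed = 120 × p × (1 − s)

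With s = 60%:

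| True rate | Expected cases | Missed |
|---|---|---|
| 5% | 6 | 2.4 |
| 10% | 12 | 4.8 |
| 20% | 24 | 9.6 |

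**Illustration of the effect on a true difference.** Assume true rates of 20% and 10%, with 40% treated in both arms. The recorded rates are 0.20 × 0.4 = 8% and 0.10 × 0.4 = 4%. The risk difference falls from 10 to 4 points, while the risk ratio stays at 2.0. With 60 per arm and a two-sided Fisher test at 0.05 (exact enumeration), power falls from about 25% to about 6%.

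**Illustration of unequal readiness to treat.** Assume no true difference.

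- True rate 15%, with 70% treated in one arm and 40% in the other: recorded rates are 10.5% and 6.0%, a false difference of 4.5 points. Fisher p < 0.05 occurs about 7% of the time.
- 80% versus 60% treated: the apparent risk ratio is 0.60 / 0.80 = 0.75. Fisher p < 0.05 occurs 0.7%, 2.6% and 5.7% of the time at true rates of 5%, 10% and 20%.
- 90% versus 50% treated: the apparent risk ratio is 0.50 / 0.90 = 0.56. The corresponding figures are 1.4%, 6.0% and 16.7%.

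At low event rates the harm is therefore mostly missed events and a biased estimate, more than a false-positive test.

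**The case against.** **The plan names a sedation scale for over-sedation.** This stands in part. The scale may already identify the event, with treatment as a further condition. The coded variable is still treatment, though, and neither a cut-off nor a combining rule is given. That treatment is a necessary condition is the likeliest reading, not a certainty.

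**Blinding is not mentioned anywhere.** A reader might infer that an unblinded nurse, who also charted the pump every hour, treated the arms differently. The documents do not support that as fact. Lack of masking is an inference from the light and the beep. The nurse who decided treatment and the nurse who charted pump use are not said to be the same person. Both are described as outside the study team, which lowers the risk of arm-dependent behaviour without removing it.

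**Scores may carry the same bias.** This stands. The documents do not say who scored sedation or whether that person was masked. A scheduled score captures untreated events, but it cannot be claimed to remove arm-dependent behaviour.

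**Oximetry values may not be available.** This also stands. Continuous monitoring is stated, but charting of saturations or respiratory rates in the EHR is not.

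**Treated events are a reasonable filter for clinical importance, and the outcome is secondary.** Both are fair. The filter is openly described, the primary outcome is satisfaction, and opioid consumption is measured directly. Power of about 25% even with full capture, under the 20% versus 10% assumption, means that the comparison is largely descriptive either way. Accurate description is still the reason to count the charted events.

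**Conclusion.** The concern holds in this form. As written, the outcome counts over-sedation and respiratory depression through treatment, and over-sedation that was charted but untreated is likely to be missed. This rests on reading treatment as necessary for an event to count, and on some over-sedated children having had no treatment coded. The documents cannot show how often that happened. Every magnitude above is illustrative.

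Two stronger readings are tempting and should not be drawn: that the arms were in fact assessed differently, and that this was the trial's designated safety outcome. No evidence of a difference in nurse behaviour is given, and the text calls this a secondary outcome on opioid-related side effects. The point is a worthwhile improvement to a secondary outcome and does not touch the primary analysis.

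**What to change.** 1. Report over-sedation per patient and POD as any charted score in the named scale's own over-sedated category, whether or not treatment was given. The documents do not reproduce the scale, so the sponsor should state the category from its source.
2. Keep the existing treated yes/no outcome beside it, state how score and treatment relate, and describe it as treatment rather than incidence.
3. For respiratory depression, establish whether saturation or respiratory values were charted in the EHR. If so, define the event from those values in the same way, with the criterion set by the sponsor. If not, label the outcome as treated respiratory depression.
4. State that treatment decisions, and possibly the scores, were made by staff not known to be masked, so that arm-dependent ascertainment remains a limitation.

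For over-sedation this uses scores the plan says were already recorded. It needs no new assessment and can be done retrospectively by the coordinator who already extracts EHR data. The cost is some extra extraction time and a few lines of text.
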